Patients will be assigned to either the control group (TENS unit) or the experimental group (Neubie) through a randomization process: All subjects will be assigned a number as they are cleared through the screening process. We will use a randomization schedule to assign these numbers, created with the Graphpad randomization calculator web application (https://www.graphpad.com/quickcalcs/index.cfm). We will use the block randomization method to build two groups of equal size, with a block size of 4. This method will satisfy our need for two equal groups sizes, control and experimental.

Participants will then undergo a specialized radiculopathy protocol that includes traditional PT therapy with the Neubie (experimental group) or TENS unit (control group) being used during PT exercises. Both the experimental and control group subjects will undergo 12 30-minute sessions of physical therapy over a 6-week period which include pre-set physical therapy exercises. We hypothesize that treatment with the NEUBIE device twice a week for 6 weeks will result in improvement Visual Analogue Scale (VAS) score, Oswestry Disability Index questionnaire score, Straight Leg Raise Test degrees of movement, improved outcomes in Electrophysiological findings of Tibial H-Reflex, and presence of degree of spontaneous electrical activity such as fibrillation potentials and positive sharp waves of muscles innervated

by L4, L5, and S1 nerve roots, and improvement in a patient satisfaction questionnaire score. These variables will provide both quantitative and qualitative data on the severity of radiculopathy symptoms (see "Tools for data collection" below).

Sample size: A power analysis was performed to determine appropriate minimum sample size for recruitment. Based on a power analysis using G*Power, we will analyze our data using a repeated measures ANOVA for within-subject factors (baseline vs post treatment). A sample size of 64 subjects per group (TENS unit or Neubie device) is sufficient to detect a clinically important difference between timepoints assuming an effect size of 0.5 between means with 80% power and a 5% level of significance. Considering a dropout rate of 10%, the sample size required will be a minimum of 141.

Data Collection Methods

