Data will be collected via observational measurements taken by staff trained specifically on EMG/NCS at Hands on Diagnostics clinic sites. Consent forms and data will be stored in a locked cabinet. Data will be kept for a period of 5 years after the final report has been produced. Thereafter, the data will be destroyed. Detailed description of these measurements is included in the methodology section. Data Analysis and manuscript preparation based on findings will be performed by [name], DPT, MD, PhD, DSc, ECS (co-PI) and [name], PhD (Director of Research at NeuFit).

Participant data will be analyzed to test for an intervention main effect and symptoms at beginning and end of treatment completion (time x intervention). Measurements at the final treatment session will be compared to baseline with an ANOVA (significant changes in EMG/NCS – baseline vs session #) as a within-subject factor.

Tools for Data Collection

Time commitment for participants: 12 hours over 6 weeks (1-hour sessions, frequency detailed below).

Materials Needed:

NEUBIE device

Electrodes

Carbon Fiber Pad

AMBU Nerve Conduction Study disposable skin electrodes

AMBU EMG needle electrodes

Alcohol wipes

Cadwell Summit EMG device

Needle Disposal Receptacle

Intervention/Treatment Protocol

Neurostimulation pads (either rectangular or circular carbon fiber) are linked to electrodes (designated red and black) for paired placement on the skin. Pad colors determine polarity of electrical current (Red = positive, Black = negative; typical direction of electron current flow is Black to Red).

Standardized pad placement: Rectangular electrodes attached to the red leads will be placed on the myotome of affected nerve (as determined by EMG). To address distal denervation, the rectangular electrodes attached to the black leads will be placed on the Tibialis Anterior muscle for cases of L4 radiculopathy, Extensor Digitorum Brevis muscle (EDB) on the dorsum of the foot for cases of L5 radiculopathy and the Soleus muscle for cases of S1 radiculopathy, as indicated by EMG findings. When multiple levels involved, then the most distal muscle will be selected.

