Standardized training frequencies: Electrical frequencies used are standardized via NeuFit's protocols. The pulses per second (PPS) determine the type of stimulation being provided. Frequencies on the Neubie range from 1-500 PPS. The PPS designated here (500 PPS) causes a smoother stimulation (rather than intermittent contractions) that results in relaxation to support increased range of motion, nerve conduction, and stimulation of blood flow.

Training intensity: Participants will be asked to undergo e-stim with the Neubie at their "treatment threshold". Treatment threshold will be described as "uncomfortable," but not "painful" (a 5-7 out of 10 on a perceived intensity scale). While being stimulated, participants will be asked to undergo a variety of PT exercises to mobilize their hips, legs, feet and ankles.

Duration of sessions: Roughly 45-60 minutes per session – 30 minutes of stimulation (either Neubie OR TENS application) + physical therapy exercises + time for clinical measurements/outcome measures.

At the end of the 12 sessions of treatment, subjects receive a final evaluation session that includes a Visual Analogue Scale (VAS) score, Oswestry Disability Index questionnaire score, Straight Leg Raise Test degrees of movement, Electrophysiological findings of Tibial H-Reflex, and presence of degree of spontaneous electrical activity such as fibrillation potentials and positive sharp waves of muscles innervated by L4, L5, and S1 nerve roots, and a patient satisfaction questionnaire score.

Outcome Measures

Pre and post treatment paradigm (at baseline and at 6 weeks), the following variables will be evaluated: Visual Analogue Scale (VAS) score, Oswestry Disability Index questionnaire score, Straight Leg Raise Test degrees of movement, Electrophysiological findings of Tibial H-Reflex, and presence of degree of spontaneous electrical activity such as fibrillation potentials and positive sharp waves of muscles innervated by L4, L5, and S1 nerve roots, and a patient satisfaction questionnaire score.

Procedures and Risks

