Risks associated with participation in this study are minimal and no greater than those experienced during a routine physical therapy intervention. Both AC and DC stimulation has been employed in physical therapy practice for over 15 years. Risks associated with electrical stimulation include mild discomfort caused by the sensation of the electrical stimulation (buzzing, tingling), and possible delayed onset muscle soreness (DOMS) after sessions.

This therapy is non-invasive, and stimulation intensity is governed by the participant. The patient will be asked to tolerate some discomfort with a perceived intensity level of 5 out of 10 but will never be asked to tolerate intensity that causes pain. Further, they will be monitored for the duration of the sessions by their practitioner and will never be left alone while being stimulated.

Potential Benefits

Participants will receive electrical stimulation treatments specifically in the lower back and leg regions. This 12-session course of treatments may decrease symptoms associated with radiculopathy, including nerve damage related weakness, numbness, and pain. Such improvements in pain could significantly benefit participants quality of life and physical mobility.

Benefit to Society The use of a non-invasive medical device like the Neubie for treatment of peripheral neuropathy could have several major benefits. Most substantially, it could validate a treatment that could be used in both a clinic setting, or with proper training, at home by patients, to keep radiculopathy related symptoms from worsening or reoccurring. It could also help in understanding the use of electrical stimulation in rehabilitation from neurological disease, nerve damage, and neuropathic pain.

Data Safety Monitoring

The study does not have a data and safety monitoring board, but the researchers have an internal plan for data and safety monitoring. Safety information will be collected by staff at Neufit and Hands On Diagnostics. All personnel involved with patient interactions will have completed necessary HIPAA training.

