Safety data collection will start from recruitment and will be collected at each treatment session. The data, specifically patient health and response to treatment, will be reviewed by the Pls monthly. Research will be suspended if there is any indication of injury or increased pain to participants. Patients will be withdrawn early from the study if there is an indication that they are unable to comply with the protocol or there are any safety concerns related to side effects of the e-stim. If withdrawn early due to safety concerns, clinical evaluation by a physician may be necessary to evaluate for additional health issues.

Population and Sample

Inclusion criteria:

- 1. Must show evidence of lumbo-sacral radiculopathy as determined by EMG and straight leg raise test.
- 2. Must be able to attend weekly sessions for the 6-week period of the study (no extended travel)
- 3. Must be at least 18 years old.

Exclusion criteria:

- 1. Currently pregnant
- 2. Cardiac pacemaker
- 3. Active or recent cancer
- 4. Active or recent blood clots
- 5. History of epilepsy
- 6. Open wounds
- 7. Spinal fusion surgery

Participant Recruitment

Participants will be recruited from existing clinic patient population who seek treatment for radiculopathy. Any patient meeting the criteria who contacts any of the study sites will be told about the study and will be provided with a copy of the informed consent to review. Clinic Managers will handle enrollment at their respective sites. During phone or in person consultation, patients who are interested in joining the study will be required to enroll and submit the signed informed consent form prior to their evaluation visit.

No incentive will be offered or provided for the study beyond treatment outcomes.

Privacy and Confidentiality

Initial recruitment may occur over the phone, but all additional consent processes and procedures will occur behind closed doors in private treatment rooms with only staff involved in conducting the study present to minimize the risks of privacy.

Results of this study may be used in publications and presentations. The study data will be handled as confidentially as possible. Individual names and personal identification information will not be collected at any point. Data may be shared for use in future studies or with other researchers. In this case, any personal identifying information of participants will not be

	nc	Ι		_	_	
ır	יזו		$\boldsymbol{\alpha}$	$\boldsymbol{\Delta}$	n	

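### The plan specifies no masking of the straight leg raise, H-reflex and EMG examiners and no coded-arm analysis, although the devices differ visibly and the analysts are the co-PI and the device company's Director of Research

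*Combined protocol and SAP*

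**What the plan says.** Under Research Design and Methodology, participants are randomised in blocks of 4 to the Neubie or a TENS unit. Procedures and Risks says of participants under stimulation that "they will be monitored for the duration of the sessions by their practitioner", so the treating person knows the arm.

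On measurement, Data Collection Methods says: "Data will be collected via observational measurements taken by staff trained specifically on EMG/NCS at Hands on Diagnostics clinic sites". Outcome Measures lists three quantities that staff obtain (straight leg raise in degrees, tibial H-reflex, and spontaneous activity on needle EMG) and three that the participant reports (VAS, Oswestry, satisfaction). The session-duration paragraph of Intervention/Treatment Protocol counts within a session "physical therapy exercises + time for clinical measurements/outcome measures". That section and Setting of the Research also describe a final evaluation session after the 12 treatments, whereas Data Collection Methods compares measurements at the final treatment session with baseline.

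On analysis, Data Collection Methods says "Data Analysis and manuscript preparation based on findings will be performed by" the co-PI and NeuFit's Director of Research. The tests named there are an intervention main effect and time x intervention.

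On access during the trial, Data Safety Monitoring says "Safety information will be collected by staff at Neufit and Hands On Diagnostics". It adds: "The data, specifically patient health and response to treatment, will be reviewed by the" PIs each month. It does not say whether that review is by arm.

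The document contains no statement on masking. The word blind, in any form, occurs only in titles in the reference list.

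**The concern.** Straight leg raise in degrees and the presence or degree of spontaneous EMG activity depend on the examiner's reading. EMG and straight leg raise are eligibility tests, and participants receive their number once they clear screening, so that measurement precedes allocation. The final measurement follows it. An examiner who expects more from one device can therefore move only the later value, and that movement goes straight into the time x intervention term, where it looks the same as a treatment effect.

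The examiner-obtained outcomes are also the ones that masked assessment can protect. If they are taken unmasked, they lose much of their value as a check on VAS, Oswestry and satisfaction, which come from participants for whom no masking is described.

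At the analysis stage, one analyst is employed by the device company and the other is an investigator. No primary outcome is named among the six measures, so the analysts have discretion that coded arms would limit.

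**Working it through.** **1. The plan's own figure.** Inputs from the sample size paragraph of Research Design and Methodology: standardised effect 0.5, power 80%, level 5%, 64 per group, dropout 10%, minimum total 141.

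- A two-sample t-test, two-sided at 5%, with d = 0.5 and 80% power, needs 63.8 per arm, so 64. Power at 64 is 80.1%. The stated 64 reproduces.
- The plan does not state sidedness. A one-sided two-sample test would need 51 per arm, and a paired baseline-to-post test 34 in all. The two-sided between-arm test is the reading that matches.
- Total: 2 x 64 = 128, and 128 x 1.10 = 140.8, so 141. Dividing by 0.90 gives 142.2, so 143. The gap of 2 does not affect this point.

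**2. What a differential shift would do.** With two time points, the time x intervention test compares change between arms. Suppose there is no true difference, and measurement shifts one arm's mean by b SD of the quantity compared. With n = 64 per arm:

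- degrees of freedom = 2 x 64 - 2 = 126
- noncentrality = b x sqrt(64/2) = b x 5.657
- false-positive rate = P(|T| > t(0.975; 126)), with T noncentral t

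| Assumed shift b (SD) | Share of planned 0.5 | Noncentrality | Two-sided false-positive rate |
|---|---|---|---|
| 0 | 0% | 0 | 5.0% |
| 0.05 | 10% | 0.283 | 5.9% |
| 0.10 | 20% | 0.566 | 8.7% |
| 0.20 | 40% | 1.131 | 20.2% |
| 0.30 | 60% | 1.697 | 39.2% |

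The shifts are assumptions; no figure in the documents supports or excludes any of them. The calculation is for one continuous outcome, such as straight leg raise in degrees. It does not apply to spontaneous EMG activity, which is recorded as present or graded.

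**3. Which safeguards the text contains.**

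| Step | Who | Safeguard stated |
|---|---|---|
| Stimulation | Practitioner, present throughout | None described; this person knows the arm |
| Straight leg raise, H-reflex, EMG | EMG/NCS-trained staff | None; not said to be separate from the practitioner |
| VAS, Oswestry, satisfaction | Participant | None; setting of completion not stated |
| Monthly review | PIs | Not stated whether by arm |
| Analysis and manuscript | Co-PI and company Director of Research | None; coding of arms not mentioned |

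**4. Effect of the fix on sample size.** Masking and coding change none of the inputs in step 1, so 64 per group and 141 in total stand.

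**The case against.** The strongest reply is that silence is not evidence of unmasked practice. The document says who measures and who analyses. It does not say that examiners are told the arm or that the analysis file carries arm names. A reader might infer that assessors and analysts know the arm. The text does not establish that, and this part of the objection stands: what can be said is that no safeguard is specified.

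A reader might also infer that masked assessment needs no additional staff, because EMG/NCS-trained people and a final evaluation session already exist. The documents do not support this. They never say that assessing and treating staff are different people, they give no staffing by site, and they are inconsistent on whether the last measurement falls in a separate session. A separate session would not in any case mean a separate examiner. A masked assessor at every clinic could require another person, so it is not asked for here.

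Third, the false-positive figures are general: any trial of this size with such a shift would show them. That is correct. They indicate how sensitive the comparison is and do not estimate the bias in this trial.

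Finally, coding arms at analysis may achieve little if the monthly review has already shown an investigator the response by arm. That also stands, and the fix has to cover the review.

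None of this closes the gap. A team that follows the plan as written has no instruction to protect either step.

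**Conclusion.** The concern holds as a gap in the plan: no masking of the straight leg raise, H-reflex and needle EMG examiners is specified, and no coded-arm analysis, in a trial of two visibly different devices analysed by people with an interest in one of them. The examiner-obtained outcomes and the analysis are open to bias that could be reduced cheaply.

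The size is unknown. The range of about 9% to 39% rests on assumed shifts of 0.1 to 0.3 SD, a continuous outcome, 64 analysed per arm, no true effect and a two-sided 5% test. How far the trial's conclusion would depend on these measures is also unknown, because no primary outcome is named. The change is worth making before the final assessments are taken. It does not imply that bias has occurred, and it would leave bias in the patient-reported outcomes in place.

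**What to change.** 1. **Assessment.** State who takes the final straight leg raise, H-reflex and needle EMG measures. At sites where existing EMG/NCS staff do not treat the participant, have them take these measures without being told the arm and with the device out of sight. Record for every participant whether the assessor was masked, and report a sensitivity analysis restricted to masked assessments. That subset is smaller, and where masking failed after allocation it is no longer a purely randomised comparison, so it should be read as supportive.
2. **Participant forms.** Have participants complete VAS, Oswestry and satisfaction without the treating therapist. This removes the therapist's presence but not the participant's own knowledge of the device.
3. **Analysis and review.** Give the analysts arms coded A/B until the analysis is locked. Keep outcome data by arm out of the monthly PI review, except where safety requires it.

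The cost is protocol wording, one form field and some scheduling effort at small clinics. Sample size is unchanged. Sites without a non-treating examiner need no new staff under this wording; they record that the assessment was unmasked.

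### The only planned analysis, an ANOVA of change, suits neither a present/absent or graded EMG finding nor, if latency is the measure, an H-reflex that may be absent; a baseline-adjusted comparison between arms should replace it.

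*Combined protocol and SAP*

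**What the plan says.** The sample size paragraph under Research Design and Methodology states one method for all outcomes: "we will analyze our data using a repeated measures ANOVA for within-subject factors (baseline vs post treatment"). The analysis paragraph under Data Collection Methods adds an intervention effect on "symptoms at beginning and end of treatment completion (time x intervention") and then applies an ANOVA of final against baseline measurements to the nerve tests, naming "significant changes in EMG/NCS" as its object, with baseline against a later session as the within-subject factor.

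Under Outcome Measures, the needle EMG outcome is "presence of degree of spontaneous electrical activity such as fibrillation potentials and positive sharp waves" in L4, L5 and S1 muscles, which I read as presence or degree. The other nerve outcome is "Electrophysiological findings of Tibial H-Reflex". There is no grading scale, no rule for combining muscles, roots or sides, no H-reflex parameter and no rule for an absent response. The protocol says its variables yield qualitative as well as quantitative data, but gives no method for the qualitative ones.

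The first inclusion criterion is "Must show evidence of lumbo-sacral radiculopathy as determined by EMG and straight leg raise test". The intake electrophysiology also serves as the baseline (Setting of the Research; Research Design and Methodology).

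**The concern.** Three separate problems follow.

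- **Scale.** Presence is yes/no and degree is a short ordered grade. An average change treats the steps as equal. On a yes/no score it also pools participants who can only stay or improve with participants who can only stay or worsen.
- **Selection.** Participants enter partly because an EMG was abnormal, and that same test is the baseline. A repeat test can look better with no treatment effect. The baseline-versus-final contrast, in which the sample size paragraph frames its target, cannot separate this from benefit.
- **Undefined values.** An absent reflex has no latency. If latency is the parameter, a participant who regains or loses the reflex has no change value and leaves the analysis.

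At stake is what can be concluded from two of the six listed outcomes, the two that measure nerve function directly.

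**Working it through.** **1. The plan's own figure.** Inputs from the sample size paragraph: effect size 0.5, power 80%, 5% significance (taken as two-sided), two equal groups. A two-sample t-test needs 63.77, so 64 per group, with power 0.801. With 10% added, 128 × 1.10 = 140.8, so 141. The stated figures reproduce as a comparison of two continuous means.

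**2. The same 64 per arm on a yes/no finding.** The documents give no EMG rates, so every rate below is an assumption. With all participants positive at baseline:

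power = Φ{[|p1 − p2|√n − 1.96√(2p̄(1 − p̄))] / √[p1(1 − p1) + p2(1 − p2)]}

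For persistence of 90% against 70%: (0.2 × 8 − 1.96 × 0.566) / 0.548 = 0.90, so power is 0.815.

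| Persistence, TENS vs Neubie | Power at 64 per arm | Needed per arm for 80% |
|---|---|---|
| 90% vs 70% | 0.815 | 62 |
| 80% vs 60% | 0.699 | 82 |
| 70% vs 50% | 0.639 | 93 |
| 80% vs 70% | 0.255 | 294 |

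**3. The planned time-by-intervention test on that score.** With two visits this is a two-sample test of change. Simulation: 20,000 runs, 64 per arm, and 5% new onset among baseline negatives.

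| Positive at baseline | Persistence | Type I error (both arms at the higher rate) | Power |
|---|---|---|---|
| 100% | 70% vs 50% | 0.052 | 0.65 |
| 100% | 90% vs 70% | 0.048 | 0.82 |
| 70% | 70% vs 50% | 0.050 | 0.39 |
| 70% | 90% vs 70% | 0.045 | 0.58 |

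Most of the fall in power is dilution: only 0.70 × 64 = 44.8 participants per arm can improve, and a 20-point effect in them averages 0.70 × 20 = 14 points over the arm. Adjusting for baseline instead of using change recovers part of it, about 3 to 7 percentage points with 50% to 85% positive at baseline under the rates tried. The gain shrinks as that share nears 100% and is nil when all are positive.

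**4. The within-arm test.** Suppose all are positive at baseline and 10% test negative at 6 weeks purely on re-testing. The mean change is −0.10, its standard error is √(0.10 × 0.90 / 64) = 0.0375, and the ratio is 0.10 / 0.0375 = 2.67, beyond 1.96. Each arm would be expected to show a significant improvement with no treatment effect in either.

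**5. H-reflex, if latency is analysed.** Assume a share *a* absent at baseline, recovery of 30% (Neubie) vs 10% (TENS), and loss *l* by week 6 of 5% vs 10%. Pairs per arm = 64 × (1 − a) × (1 − l). For a = 20%, TENS has 64 × 0.80 × 0.90 = 46.1 and Neubie 64 × 0.80 × 0.95 = 48.6. Their harmonic mean is 47.3, and power for d = 0.5 is Φ(0.5√(47.3/2) − 1.96) = 0.68. The same normal approximation gives 0.81 with all 64.

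| Absent at baseline | Pairs, TENS / Neubie | Power, d = 0.5 | Recoveries omitted, Neubie / TENS | Losses omitted, Neubie / TENS |
|---|---|---|---|---|
| 10% | 51.8 / 54.7 | 0.73 | 1.9 / 0.6 | 2.9 / 5.8 |
| 20% | 46.1 / 48.6 | 0.68 | 3.8 / 1.3 | 2.6 / 5.1 |
| 30% | 40.3 / 42.6 | 0.62 | 5.8 / 1.9 | 2.2 / 4.5 |
| 40% | 34.6 / 36.5 | 0.56 | 7.7 / 2.6 | 1.9 / 3.8 |

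The omitted outcomes favour Neubie here only because the assumed rates do. The direction in the trial is unknown.

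**The case against.** The strongest reply is that ANOVA does little harm to the comparison that matters. That largely stands. A reader might infer that the model fails by design because everyone selected on EMG starts positive. It does not: if every baseline is the same, change is the final value minus a constant. The simulated type I error is 0.045 to 0.052, and in that case a comparison of proportions has essentially the same power (0.64 to 0.82 against 0.65 to 0.82). Randomisation also balances selection and regression to the mean between arms, so these affect only the within-arm test.

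Three other strong readings are tempting and unsupported.

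- The inclusion criterion does not say which EMG abnormality qualifies. A participant who entered on another finding may still have fibrillations, so baseline presence cannot be deduced from the route of entry.
- A positive participant is limited to no change or improvement only on a yes/no score. On a grade, baseline values vary and worsening is possible.
- The protocol does not commit itself to latency. Analysing presence, or amplitude with absence scored as zero, would lose nobody. That a reflex can be absent is general neurophysiology, not a statement in the protocol.

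It is also fair to say that leaving out participants whose reflex is absent at baseline is a restriction on a pre-randomisation value. It costs scope and power but does not bias the comparison among those who remain. Only exclusions for reflexes lost by week 6 depend on a post-randomisation result.

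**Conclusion.** The point holds as a matter of fit, interpretation and power, and the change should be made. The one stated method is a comparison of means, it is applied by name to EMG/NCS, and the needle outcome is not a continuous measure. Under the assumed rates, 64 per arm gives power of about 0.64 to 0.82 for a 20-point difference when all are positive at baseline, and 0.39 to 0.58 under the planned test when 70% are. Baseline adjustment recovers a few points of that, not all of it. False positives between arms are not inflated.

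The within-arm test should not carry the conclusion, because entry and baseline rest on the same EMG.

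The H-reflex part is conditional on latency being the parameter. If it is, assumed absence of 10% to 40% at baseline lowers power for d = 0.5 from 0.81 to between 0.73 and 0.56. Recoveries and losses go uncounted, and the losses by week 6 can bias the arm comparison if they differ by arm. The protocol names no primary endpoint, so nothing here shows that the trial's main result is at risk.

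**What to change.** **Spontaneous activity.** Replace the ANOVA with a between-arm comparison of the 6-week grade in all participants, using a proportional-odds model adjusted for baseline grade, or a logistic model if only presence is recorded. Define the grading scale and the rule for combining muscles, roots and sides. Report resolution among baseline-positive participants as a supplement only; used alone, it would leave out everyone who newly develops activity.

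**H-reflex.** Name the parameter and the rule for an absent response. Use an analysis that keeps absent reflexes, for example an ordered outcome with absence as the worst category, or a rank-based analysis, in either case adjusted for baseline. Give latency in those with a reflex at both visits as a supplement.

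**Both.** State that conclusions rest on the between-arm comparison and that baseline-versus-final changes within an arm are descriptive.

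**Cost.** No extra visits or tests. EMG grade and reflex presence must be recorded on a fixed scale at both existing visits, so the definitions have to be settled for data collection as well as for analysis. Ordinal results are slightly less familiar to report than a mean change.

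### Patients withdrawn from the study by default have no 6-week outcome, which could bias both the arm comparison and the comparison with baseline; the likely size is small and the remedy cheap

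*Combined protocol and SAP*

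**What the plan says.** Data Safety Monitoring sets the withdrawal rule: "Patients will be withdrawn early from the study if there is an indication that they are unable to comply with the protocol". A second ground follows in the same sentence, this time about the stimulation itself: "or there are any safety concerns related to side effects of the e-stim". The wording removes the patient from the study, not only from stimulation. The only follow-up it mentions is a possible physician evaluation after a safety withdrawal. That is clinical care, not outcome assessment.

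Outcome Measures and Setting of the Research schedule pain (VAS), Oswestry, straight leg raise and the electrophysiology at baseline and at a final evaluation after the 12 sessions, at 6 weeks. Data Collection Methods plans an analysis of "symptoms at beginning and end of treatment completion (time x intervention" and adds: "Measurements at the final treatment session will be compared to baseline with an ANOVA".

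Some passages hint at data recorded in between. Duration of sessions includes "time for clinical measurements/outcome measures". Data Collection Methods has the phrase "baseline vs session" with a number sign after it. Data Safety Monitoring says: "Safety data collection will start from recruitment and will be collected at each treatment session", and describes the data as "specifically patient health and response to treatment". None of these schedules VAS or Oswestry before the final evaluation.

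The sample size paragraph deals with dropout only by raising the number recruited, to a minimum of 141 for 10% dropout.

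**The concern.** The trial compares two stimulation devices, and one reason for withdrawal is a side effect of stimulation. Withdrawal can therefore depend on the assigned device. Training intensity also sets an uncomfortable level for the Neubie and gives no target for TENS, so different losses are plausible, though not shown. Inability to comply has no stated threshold, and no blinding is described, so staff may judge it knowing the arm.

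Two planned analyses are exposed:

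- **Between arms.** If more patients leave one arm and would have done worse, that arm looks better than it is. The same happens with equal numbers lost if those lost from one arm would have done worse than those lost from the other.
- **Within patients, final against baseline.** If those lost would have improved less, the change among those who stay overstates the change in all patients, even when the arms lose equally.

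A larger sample preserves power. It does not remove either bias, and outcomes not collected at 6 weeks cannot be recovered later.

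**Working it through.** **The plan's own figure.** A two-sample t-test with effect size 0.5, two-sided 5% level (sidedness assumed) and 80% power needs 63.8, so 64 per arm and 128 in total. 128 × 1.10 = 140.8, so 141, as stated. (128 / 0.90 = 142.2 would give 143, a minor difference.) With 10% lost from 141, about 127 remain and power is 79.8%. The increase does its job for power.

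**Inputs for the bias.** From the plan: 141 randomised 1:1 (70.5 per arm) and 10% overall dropout. Assumed, because the documents give no figures: the share lost in each arm (d1, d2), and the gap g between the means of completers and dropouts, in SDs of the baseline to 6-week change. No true effect and no use of interim values are also assumed.

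**Formulas.**

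- Bias of the arm comparison = d1·g1 − d2·g2.
- SE = √[1/(70.5(1−d1)) + 1/(70.5(1−d2))].
- Type I error = P(Z > 1.96 − bias/SE) + P(Z < −1.96 − bias/SE).

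**Arm comparison, equal gaps (g1 = g2 = g).** For 15%/5%, SE = √[1/59.925 + 1/66.975] = 0.178. With g = 1.0, bias = 0.15 − 0.05 = 0.10 and bias/SE = 0.56, so the type I error is 8.7%.

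| Loss by arm | g = 0.25 | g = 0.5 | g = 1.0 |
|---|---|---|---|
| 10%/10% | 0; 5.0% | 0; 5.0% | 0; 5.0% |
| 12%/8% | 0.01; 5.0% | 0.02; 5.1% | 0.04; 5.6% |
| 15%/5% | 0.025; 5.2% | 0.05; 5.9% | 0.10; 8.7% |

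(Each cell: bias in SD; type I error.) The noncentral t gives 5.2%, 5.9% and 8.6% for the last row.

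**Only half of dropout informative** (7.5%/2.5% informative plus 5%/5% uninformative, total 12.5%/7.5%): bias is 0.0125, 0.025 and 0.05 SD, and type I error 5.1%, 5.2% and 5.9%.

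**Equal loss, unequal gaps.** 10% lost in each arm, with a gap of 1 SD in one arm and none in the other: bias = 0.10 × 1 − 0.10 × 0 = 0.10 SD, type I error 8.7%.

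**Comparison with baseline.** The bias in mean change is d·g. With 10% lost it is 0.10 × 0.25 = 0.025, 0.10 × 0.5 = 0.05 or 0.10 × 1.0 = 0.10 SD, whatever the split by arm.

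**What follow-up would recover.** If a share r of dropouts is reached at random and g = 1, the remaining bias per arm is d − r·d/(1 − d + r·d). At 15%/5% with r = 0.5 this is 0.0689 − 0.0244 = 0.045 SD, type I error 5.8%. With r = 0.25 it is 0.1077 − 0.0370 = 0.07 SD, type I error 6.9%. If those reached are not typical of those lost, the gain will differ.

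**The case against.** The best case against is that the numbers are small. At 12%/8%, or with only half of dropout informative, the type I error is at most 5.9% and the bias at most 0.05 SD, against a planned effect of 0.5. Only a gap near 1 SD, with losses or gaps that differ clearly between arms, moves it much further. Procedures and Risks points to few side-effect withdrawals: the participant controls the intensity, and the listed risks are mild discomfort and muscle soreness. This stands, and it keeps the point to a cheap improvement.

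A second objection is that the missing rules may exist elsewhere. Consent pages are not in the text available, the internal monitoring plan is mentioned but not shown, and interim measurements may exist. This makes the absence of follow-up less certain than the absence of an analysis set. But nothing in the documents schedules a VAS or Oswestry value for a withdrawn patient.

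Three stronger readings are tempting and not supported:

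- **That the plan will favour one device.** No dropout by arm and no outcomes of dropouts are given, so neither the existence nor the direction of a bias is shown.
- **That 15%/5% is a worst case.** Ten points is about two standard errors of a chance difference in dropout (√(2 × 0.1 × 0.9/70.5) = 0.0505). That does not bound a systematic difference between devices. A 20%/0% split with a 1 SD gap gives a bias of 0.20 SD and a type I error of about 20%.
- **That similar dropout in the two arms would settle the matter.** It would not for the comparison with baseline, nor for the arm comparison if the gaps differ.

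**Conclusion.** The point holds as a modest, conditional one. Followed as written, the withdrawal rule loses outcomes for reasons that can depend on the assigned device, and the plan does not say who is analysed or how missing values are handled. Both the arm comparison and the comparison with baseline are exposed, under the different conditions given above. On the assumed splits of 12%/8% and 15%/5% the type I error of the arm comparison stays between 5.0% and 8.7%, and near nominal unless the gap approaches 1 SD. These figures rest on assumed losses and gaps, completers only, and no usable interim values. They illustrate the size and do not bound it. The change is worth making because it is cheap now and cannot be made after the outcomes are lost.

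**What to change.** Leave every clinical decision to stop stimulation, and every safety judgement, as it is. Then:

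1. Reword Data Safety Monitoring so that stopping study treatment does not end outcome follow-up.
2. Seek the 6-week evaluation, or at least VAS and Oswestry, from every randomised patient who still consents and for whom assessment is judged suitable, including those who simply stop attending.
3. Analyse patients in the arm to which they were randomised, whatever treatment they completed, for example with a baseline-adjusted model of the 6-week value. State its assumption: given arm and baseline, patients with missing values resemble those seen.
4. Add one sensitivity analysis covering all randomised patients, for VAS and Oswestry only, in which missing 6-week values are shifted worse by a stated range, for example 0.25 to 1.0 SD, including shifts that differ by arm.

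It would also help to state whether any outcome is recorded at each session and may be used, and to report treatment stops and missing outcomes by arm with reasons. These are documentation and do not themselves reduce bias.

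**Cost.** Protocol wording, plus follow-up effort by existing staff for about 14 patients at the planned dropout (141 × 0.10 = 14.1), more if dropout is higher. Some patients will refuse a return visit, particularly one with needle EMG, hence the questionnaire fallback. The effect estimate may be smaller because poor compliers are counted.
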